## INTRODUCTION

Peritoneal surface malignancies (PSMs), arising from primary tumors such as colorectal carcinoma, ovarian cancer, appendiceal neoplasms, malignant peritoneal mesothelioma, and pseudomyxoma peritonei, represent a challenging oncologic condition associated with significant morbidity and historically poor survival outcomes. Over the last two decades, cytoreductive surgery (CRS), with or without hyperthermic intraperitoneal chemotherapy (HIPEC), has emerged as a standard-of-care strategy in selected patients, demonstrating improved overall and disease-free survival when complete cytoreduction is achieved [1–3].

CRS frequently necessitates extensive peritonectomy to remove macroscopic tumor deposits. While oncologically effective, peritonectomy disrupts the native peritoneal lining, a specialized mesothelial surface responsible for frictionless visceral movement, immunologic defense, fluid homeostasis, and rapid tissue repair [4]. Loss of this biological barrier predisposes patients to a spectrum of postoperative complications, including dense intra-abdominal adhesions, adhesive small bowel obstruction, prolonged postoperative ileus, enterocutaneous fistula formation, surgical site infection, incisional hernia, and the need for reoperation [5–7]. These complications significantly prolong hospital stay, delay adjuvant oncologic therapies, impair quality of life, and increase overall healthcare utilization.

At present, there is no universally accepted standard for peritoneal reconstruction following peritonectomy. Conventional surgical practice typically involves leaving the peritoneal defect untreated, allowing secondary healing through fibrosis. However, this process is often disorganized and pro-inflammatory, promoting excessive fibrin deposition and adhesion formation rather than structured regeneration of a functional mesothelial layer [8]. Consequently, there has been increasing interest in biologic materials that can serve as temporary peritoneal substitutes, restoring anatomic continuity while modulating the wound-healing response.

High-purity Type I collagen (HPTC)–based biomaterials have demonstrated favorable biological and mechanical properties across a range of reconstructive and regenerative surgical applications.

Collagen, the principal structural protein of the extracellular matrix, plays a critical role in cellular adhesion, angiogenesis, and tissue remodeling. When processed through stringent purification protocols, HPTC scaffolds are biocompatible, minimally immunogenic, and bioresorbable, providing a three-dimensional framework that supports orderly tissue regeneration rather than scar-driven fibrosis [9–11].

In abdominal and reconstructive surgery, collagen-based matrices have been shown to reduce infection rates, improve integration in contaminated fields, and promote functional tissue repair. Prior studies evaluating biological meshes in the context of complex abdominal wall reconstruction during CRS have demonstrated acceptable safety profiles and encouraging clinical outcomes [12].

Additionally, emerging clinical evidence from wound care and soft tissue reconstruction has shown

that HPTC-based scaffolds can significantly reduce complication rates and enhance healing outcomes when compared with alternative biological substitutes [13–16].

Surgicoll-Mesh® is a sterile, resorbable, high-purity Type I collagen-based biomaterial designed to function as a temporary regenerative scaffold [17]. When used as a peritoneal substitute following peritonectomy, it is hypothesized to provide a protective barrier between visceral surfaces, reduce fibrin-mediated adhesion formation, and facilitate organized neo-peritoneal regeneration during the critical early postoperative period. Despite strong biological plausibility and supportive evidence from related surgical domains, high-quality prospective randomized data evaluating collagen-based peritoneal substitutes in patients undergoing CRS for intraperitoneal malignancy remain limited. Given the substantial morbidity associated with post-peritonectomy complications and the absence of standardized reconstructive strategies, there exists a clear unmet clinical need for interventions that enhance intra-abdominal healing without compromising oncologic safety. This need is particularly relevant in resource-conscious healthcare systems, where reducing postoperative complications has direct implications for patient outcomes and system sustainability.

Accordingly, this prospective, multicenter, randomized controlled trial was designed to evaluate the safety and efficacy of Surgicoll-Mesh® as a peritoneal substitute following peritonectomy in patients undergoing CRS for intraperitoneal malignancies. The primary objective was to determine whether the use of a high-purity Type I collagen scaffold reduces the incidence of major postoperative intra-abdominal complications compared with standard peritonectomy closure. Secondary objectives included assessment of individual complication rates, bowel function recovery, length of hospital and intensive care stay, device-related adverse events, radiologic evidence of adhesions, and patient-reported quality of life outcomes using a validated instrument.

## **MATERIALS AND METHODS**

### **Study Design and Setting**

This study was designed as a prospective, multicenter, open-label, randomized controlled clinical trial evaluating the safety and efficacy of a high-purity Type I collagen-based biomaterial (Surgicoll-Mesh®) as a peritoneal substitute following peritonectomy in patients undergoing cytoreductive surgery (CRS) for intraperitoneal malignancies. The trial was conducted at two tertiary referral centers specializing in oncologic and reconstructive surgery.

The trial was conducted at two tertiary oncology referral centers – JSS Academy of Higher Education and Research, Mysuru and Adichunchangiri Institute of Medical Sciences, B G Nagara. The trial was registered prospectively with ClinicalTrials.gov (ID: NCT07241091) and approved by the Institutional Ethics Committee (Approval No.: AIMS/IEC/266/2025). The study was conducted in accordance with the principles of the Declaration of Helsinki, Good Clinical Practice (GCP) guidelines, and Consolidated Standards of Reporting Trials (CONSORT) recommendations [18].

Institutional Ethics Committee approval was obtained at all participating centers prior to patient enrollment.

### **Study Population**

Patients were consecutively screened for eligibility during multidisciplinary tumor board evaluation at participating centers. Adults aged 18–75 years with histologically confirmed peritoneal surface malignancy (including colorectal, ovarian, appendiceal, pseudomyxoma peritonei, or malignant peritoneal mesothelioma) scheduled to undergo cytoreductive surgery with anticipated peritonectomy, with or without hyperthermic intraperitoneal chemotherapy, were considered eligible. Additional inclusion criteria included Eastern Cooperative Oncology Group (ECOG) performance status 0–2 [19], adequate hematologic, renal, and hepatic function, and ability to provide written informed consent.

Exclusion criteria comprised known hypersensitivity to collagen-based products, active intra-abdominal infection or uncontrolled sepsis, chronic immunosuppression or long-term systemic corticosteroid therapy, pregnancy or lactation, extensive small-bowel resection precluding safe reconstruction, and emergency surgery or bowel perforation at presentation.

### **Randomization and Allocation**

Eligible patients were randomized in a 1:1 ratio to either the intervention group (HPTC peritoneal reconstruction) or the control group (standard peritonectomy closure). Randomization was performed using a computer-generated block randomization sequence with variable block sizes to ensure balanced group allocation across participating centers.

Allocation concealment was achieved using sealed, opaque envelopes opened intraoperatively after completion of cytoreduction and confirmation of peritoneal defect suitability. Due to the nature of the surgical intervention, blinding of the operating surgeon was not feasible. However, outcome assessors, radiologists evaluating imaging studies, and statisticians were blinded to treatment allocation wherever applicable.

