### **Outcome Measures**

#### **Primary Outcome**

The primary outcome was the incidence of major intra-abdominal complications within two months following surgery. Major complications were predefined as:

- Adhesive small bowel obstruction requiring intervention
- Enterocutaneous fistula
- Reoperation for intra-abdominal complication
- Grade  $\geq 3$  wound complications based on the Clavien–Dindo classification

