#### **Secondary Outcomes**

Secondary outcomes included:

- Individual complication rates, including intraperitoneal adhesions, bowel obstruction, surgical site infection, incisional hernia, and fistula formation

- Time to bowel function recovery, defined as the time to first flatus and tolerance of oral diet
- Length of intensive care unit (ICU) stay and total hospital stay
- Device-related adverse events, including infection, inflammatory reaction, or mesh-related complications
- Radiologic assessment of adhesions or obstruction using magnetic resonance imaging (MRI) at baseline, one month, and two months
- Quality of life assessment using the European Organisation for Research and Treatment of Cancer Quality of Life Questionnaire Core 30 (EORTC QLQ-C30), a validated cancer-specific instrument [20]

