### Statistical Analysis Plan

Statistical analyses were performed using SPSS version 29.0 (IBM Corp., Armonk, NY, USA). Continuous variables were assessed for normality using the Shapiro–Wilk test and are presented as mean  $\pm$  standard deviation for normally distributed data or median with interquartile range for non-normally distributed data. Between-group comparisons were conducted using the independent t-test or Mann–Whitney U test for continuous variables and the chi-square test or Fisher’s exact test for categorical variables, as appropriate. Effect estimates for the primary and key secondary binary outcomes were expressed as relative risks with 95% confidence intervals. Time-to-event outcomes, including time to bowel function recovery, were analyzed using Kaplan–Meier survival curves with log-rank testing. Multivariable logistic regression analysis was performed to adjust for potential confounders, including age, primary tumor type, peritoneal cancer index score, and use of hyperthermic intraperitoneal chemotherapy. All statistical tests were two-sided, and a p-value  $< 0.05$  was considered statistically significant. Analyses were conducted on an intention-to-treat basis.

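### Allocation is balanced across two centres, but the primary test, the relative risk and the log-rank test do not account for centre; if the centres differ, the test is conservative and loses a little power

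*Combined protocol and SAP*

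**What the plan says.** Under Randomization and Allocation, "Eligible patients were randomized in a 1:1 ratio" by a computer-generated "block randomization sequence with variable block sizes to ensure balanced group allocation across participating centers". Study Design and Setting gives two sites: "The trial was conducted at two tertiary referral centers specializing in oncologic and reconstructive surgery". How the 60 patients divide between them is not stated.

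Under Primary Outcome, "The primary outcome was the incidence of major intra-abdominal complications within two months following surgery", which is a yes/no composite. The Statistical Analysis Plan section compares such outcomes by the chi-square or Fisher's exact test "for categorical variables, as appropriate". It reports relative risks with 95% intervals and analyses bowel recovery by Kaplan–Meier "survival curves with log-rank testing". No strata are named for any of these. A multivariable logistic model adjusts for age, tumour type, peritoneal cancer index and HIPEC. Centre is not in that list, although the list is worded as non-exhaustive.

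**The concern.** When randomisation forces balance within a factor, that factor cannot contribute to the chance difference between arms. An analysis that ignores it still counts the between-centre spread in outcome as noise, so its standard error is too large. P-values then run high and intervals run wide.

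A centre effect is plausible here. Cytoreductive surgery follows institutional protocols, and control defects are managed by institutional practice. At stake are a few points of power in a trial with little to spare, and a primary analysis that does not match its own design. The open choice between chi-square and Fisher adds a second loose end on the same test.

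**Working it through.** **1. The plan's own sample-size figure.** Inputs from Sample Size Calculation: p1 = 0.40, p2 = 0.20, two-sided alpha 0.05, power 80%. The stated formula gives n = 7.849 × (0.40 × 0.60 + 0.20 × 0.80) / 0.20² = 7.849 × 0.40 / 0.04 = 78.5, so 79 per group. The stated 26 does not reproduce. With the 30 per arm enrolled, power is about 39%. This is a separate defect, and it sets the baseline for what follows.

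**2. Why ignoring centre makes the test conservative.** With two equal centres and complication rates a and b under no treatment effect, the unstratified variance is proportional to p(1−p), where p = (a+b)/2. If arms are balanced within centre, the correct quantity is the average of a(1−a) and b(1−b), which is smaller. Take an overall rate of 30% and a between-centre odds ratio of 3, so a = 0.189 and b = 0.411:

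- average of 0.189 × 0.811 and 0.411 × 0.589 = (0.153 + 0.242)/2 = 0.198
- ratio to 0.30 × 0.70 = 0.21: about 0.94
- effective critical value 1.96/√0.94 ≈ 2.02, a two-sided error of about 4.3%

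Exact enumeration gives 4.2%.

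**3. Size of the effect.** Exact binomial enumeration, 15 per arm in each centre (assumed split). Power is for overall rates of 40% versus 20%, type I error for a common 30%. The centre odds ratio is assumed and is the same in both arms. The chi-square has no continuity correction.

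| Centre odds ratio | Control rates | Chi-square power | CMH power | Gain (points) | Chi-square type I error |
|---|---|---|---|---|---|
| 1 | 40%, 40% | 39.3% | 39.6% | 0.3 | 4.9% |
| 2 | 32%, 48% | 39.1% | 40.4% | 1.3 | 4.6% |
| 3 | 27%, 53% | 38.9% | 41.7% | 2.8 | 4.2% |
| 4 | 24%, 56% | 38.7% | 42.8% | 4.1 | 3.9% |
| 6 | 20%, 60% | 38.3% | 44.4% | 6.1 | 3.4% |

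CMH holds 4.9% to 5.0% throughout. A 20/10 split per arm is similar (odds ratio 3: 38.9% versus 41.3%).

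**4. Cross-check with a constant relative risk of 0.5.** Null rates are 0.75 times the control rates in both arms. Chi-square versus CMH power by simulation:

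- control rates 48%/32%: 39.3% versus 40.3%, chi-square type I error 4.7%
- 55%/25% (odds ratio 3.7): 38.8% versus 41.9%, type I error 4.2%
- 60%/20% (odds ratio 6): 38.6% versus 43.8%, type I error 3.8%. The null rates here are 45%/15%, an odds ratio of 4.6, which is why this error is above the 3.4% in the table.

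**5. If there was one list for both centres.** With a single blocked list and no centre strata, the chi-square type I error stays at about 4.9% even at 55%/25% and 60%/20%. CMH still gains about 2 to 4 points of power at those two differences.

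**6. What stratifying does to the required size.** Per-arm n for 80% power falls from 79 to about 77 (odds ratio 2), 74 (3) or 68 (6), all well above 30.

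**7. The chi-square/Fisher choice.** In the design of step 3, Fisher's test has power 29.8%, 29.2% and 28.4% at odds ratios 1, 3 and 6, with type I error 2.6%, 2.2% and 1.7%. Most of that shortfall is Fisher's own conservatism, not centre, but it shows that naming one test matters.

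**The case against.** The premise is inferred. The plan describes one sequence with an aim of balance across centres. It does not say that the list was stratified or that each centre had its own, and with a single list the error distortion disappears (step 5). That objection stands, and it is why the fix begins with clarification.

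The size also rests on assumption. No document gives a centre difference, both sites are tertiary referral centres, and postoperative care was standardised across them. None of this rules out a centre effect, but odds ratios of 4 to 6 should be read as an upper range. At 2 the loss is about one point.

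A reader might infer four stronger things that the documents do not support:

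- **That false positives are inflated.** The direction is the opposite, so a positive result is not endangered by this omission.
- **That prognosis is ignored altogether.** The logistic model adjusts for four factors, which may carry part of any case-mix difference between centres.
- **That centre should simply be added to that model.** About 18 events are expected (30 × 0.40 + 30 × 0.20) for about 8 parameters, or 2.25 events each. Centre would make it 18/9 = 2.0.
- **That baseline MRI or QLQ-C30 values are wrongly discarded.** MRI is listed ("Radiologic assessment of adhesions or obstruction using magnetic resonance imaging (MRI) at baseline, one month, and two months"), but no scale is defined. The general sentence on two-sample tests ("Between-group comparisons were conducted using the independent t-test or Mann–Whitney U test for continuous variables") does not mention MRI, and no QLQ-C30 baseline is stated.

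**Conclusion.** The point holds as a modest mismatch between design and analysis. Balance across centres is an aim of the randomisation, and the primary test, its relative risk and the log-rank test take no account of centre. If allocation was balanced within centre and centre is prognostic, the planned chi-square test is conservative: type I error is about 4.6% to 4.7% at a centre odds ratio of about 2, about 4% at 3 to 4, and 3.4% to 3.8% in the largest scenarios. Power lost is about 1, 3 to 4, and 5 to 6 points respectively. With no centre effect, nothing is lost.

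These figures assume 30 per arm, 40% versus 20%, an assumed split between centres and no treatment-by-centre interaction. The change is worth making because it is cheap and matches the analysis to the design. It does not rescue power: even at an odds ratio of 6 the stratified test reaches only about 44%, against the 80% intended.

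**What to change.** 1. State in Randomization and Allocation whether each centre had its own list, and give the number of patients per centre and arm.
2. Name one primary analysis in place of the chi-square/Fisher choice: the CMH test stratified by centre, with the Mantel-Haenszel relative risk and risk difference and their 95% intervals.
3. Stratify the log-rank test by centre.
4. Leave the covariate list of the logistic model as it is for this purpose.

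The cost is wording in the analysis plan; centre is known for every patient and no new data are needed. The document is written in the past tense, so timing matters. If unblinded analysis has already been done, keep the planned test as primary and report the centre-stratified result as a labelled sensitivity analysis. The sample-size figure needs its own correction.

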### **Intervention Group: HPTC Peritoneal Reconstruction**

In patients randomized to the intervention arm, peritoneal defects created following peritonectomy were reconstructed using HPTC (Surgicoll-Mesh®), a sterile, resorbable, high-purity Type I collagen scaffold. The mesh was tailored intraoperatively to match the dimensions of the peritoneal defect and secured using interrupted absorbable sutures to adjacent tissue margins prior to abdominal closure.

The biomaterial was applied without tension and without overlap onto visceral organs.

The mesh was intended to function as a temporary biologic barrier and regenerative scaffold, facilitating organized tissue remodeling during the early postoperative period [9–11].

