### **Control Group: Standard Peritonectomy Closure**

Patients allocated to the control arm underwent standard peritonectomy closure without the use of any peritoneal substitute or biomaterial. Peritoneal defects were left untreated, allowing secondary healing according to standard institutional practice.

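### The only stated reason for not blinding concerns the surgeon; patient blinding looks feasible, is not described, and its absence leaves the QLQ-C30 open to reporting bias

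*Combined protocol and SAP*

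**What the plan says.** Study Design and Setting describes a "prospective, multicenter, open-label, randomized controlled clinical trial". Randomization and Allocation gives one reason for incomplete blinding: "Due to the nature of the surgical intervention, blinding of the operating surgeon was not feasible". It then says that "outcome assessors, radiologists evaluating imaging studies, and statisticians were blinded to treatment allocation wherever applicable". Patients are in neither statement, and no step to keep allocation from them is described.

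The same section says that allocation was concealed in "sealed, opaque envelopes opened intraoperatively after completion of cytoreduction and confirmation of peritoneal defect suitability". In the intervention arm the mesh was "secured using interrupted absorbable sutures to adjacent tissue margins prior to abdominal closure" (Intervention Group). Controls had "standard peritonectomy closure without the use of any peritoneal substitute or biomaterial" (Control Group).

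Secondary Outcomes has six entries. One is the EORTC QLQ-C30, a questionnaire that the patient completes. Another is "Time to bowel function recovery, defined as the time to first flatus and tolerance of oral diet"; the section does not say who records either event. The primary outcome is a composite of clinical complications within two months.

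**The concern.** The justification covers one person, the operating surgeon. It does not extend to the patient, who is under surgery when the envelope is opened and when the mesh is placed. For the QLQ-C30 the patient is in effect the outcome assessor. If patients know their arm, the statement that outcome assessors were blinded cannot hold for that endpoint.

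Knowing that one received a new implant, or nothing, may shift the answers. Such a shift follows allocation itself, so it cannot be separated from a mesh effect afterwards. The regression in the Statistical Analysis Plan adjusts for age, tumor type, peritoneal cancer index and HIPEC. None of these carries information on what the patient knew, so the adjustment cannot remove it.

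**Working it through.** The plan gives no figure for this bias, so there is none to reproduce. The check is mainly a comparison of passages.

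**Who is blinded**

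| Party | Status in the text | Reason given |
|---|---|---|
| Operating surgeon | Not blinded | Nature of the surgery |
| Outcome assessors, radiologists, statisticians | Blinded, where applicable | Not needed |
| Patients | Not mentioned; trial labelled open-label | None |

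**Whether patient blinding looks feasible**

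1. Allocation becomes known only during surgery, after cytoreduction (Randomization and Allocation).
2. The mesh is internal, resorbable and sutured in place before closure (Intervention Group).
3. Controls also undergo cytoreduction and peritonectomy, and their defects are left untreated (Control Group).
4. Both arms therefore have the same kind of major operation, no sham procedure is needed, and nothing described would show the patient which arm was assigned.

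**Which outcomes are exposed**

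- QLQ-C30: clearly patient-reported; one of the six secondary entries.
- Bowel recovery: exposed only if first flatus is taken from the patient's report. Tolerance of oral diet can be observed by staff.
- Primary composite: not patient-reported, so not directly affected by this route.

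**Illustration on assumed values**

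Suppose there is no true effect on a quality-of-life score, 30 patients per arm (Sample Size Calculation), a two-sided 5% test (Statistical Analysis Plan), and a pure reporting shift of b standard deviations between the arms. The values of b are assumptions, not taken from the documents. In the normal approximation:

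- standard error of the difference in SD units = √(2/30) = 0.258
- δ = b / 0.258
- probability of a significant result = Φ(δ − 1.96) + Φ(−δ − 1.96)

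| Assumed b (SD) | δ | Chance of p < 0.05 with no true effect |
|---|---|---|
| 0 | 0 | 5.0% |
| 0.1 | 0.39 | 6.7% |
| 0.2 | 0.77 | 12.1% |
| 0.3 | 1.16 | 21.3% |
| 0.5 | 1.94 | 49.1% |

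The formula is symmetric in the sign of b, so the table says nothing about direction. It shows only how the error rate would respond if a shift of that size existed.

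**The case against.** The strongest reply is that this is a gap in reporting rather than a shown bias. A reader might infer that patients were told their arm. No section says so: it is an inference from the open-label label and from the silence on patients. The label alone does not settle each party's status, since three other parties are listed as blinded in the same trial. The consent pages are not in the public text, so what patients were told cannot be checked. This stands, and the point is worded accordingly.

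A reader might also infer that leaving patients unblinded had no benefit. A missing reason does not show that none existed. Device-related events, including inflammatory reaction, are a secondary outcome, and collagen hypersensitivity is an exclusion. Withholding knowledge of an implant therefore raises safety-reporting and ethical questions. That stands too, and it is why a code break and disclosure in the consent belong in the remedy.

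Two further readings are not supported. One is that length of stay is biased by the same route. The documents do not link it to patient report, and decisions by an unblinded treating team would remain even if patients were blinded. The other is that the primary composite is a safe refuge because patients do not report it. Reoperation, and obstruction that counts only if it leads to an intervention, may reflect decisions by the surgeon, who knows the arm.

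Finally, the text is in the past tense and says that 30 patients were enrolled in each arm. If treatment is complete, only the reporting part of the fix remains. None of this supplies a reason for omitting patient blinding where it looks feasible.

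**Conclusion.** The point holds as a low-cost improvement, not a major flaw. The plan declares the trial open-label, gives a reason that covers only the surgeon, and describes a procedure in which patient blinding looks feasible. The QLQ-C30, one of six secondary entries, is left open to reporting bias. Bowel recovery is a possible second, depending on who records first flatus.

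The conclusion rests on two assumptions: that the open-label label and the silence on patients mean allocation was not withheld from them, and that no practice outside the documents would reveal the arm in any case. The documents support saying that these results may be biased. They do not support saying that they are, by how much, or in which direction.

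**What to change.** 1. State in Randomization and Allocation whether patients were blinded, and justify it if not. State also who administers the QLQ-C30 and who records flatus and diet, and whether those people know the arm.
2. For any patient still to be treated, withhold allocation from the patient and from those staff until the existing 60-day visit. Provide a code break for clinical need, including suspected device-related events, and disclose the arrangement in the consent.
3. For patients already treated who knew their arm, report the QLQ-C30, and any self-reported bowel recovery, as unblinded and interpret them cautiously.

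Cost: changes to the consent wording and to the handling of the operation note. No extra procedure is needed, and since outcome assessors are already meant to be blinded, no extra staff should be needed. The downside is that patients learn whether they received the implant only at day 60 or on code break. The third step needs no new data beyond establishing who knew the allocation.
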